The profound metabolic consequences of caloric restriction may negate some of the benefits of weight loss. Considering that calorie restriction is the preferred and most-effective strategy for the treatment and prevention of overweight and obesity and their associated comorbidities [2], strategies are needed to preserve the beneficial effects of calorie restriction while attenuating its potentially detrimental effects on metabolism, skeletal muscle, and bone. Lean mass can be preserved through increased dietary protein intake. A high dietary protein intake during energy deficiency attenuates the loss of lean mass and improves protein balance [16, 17].

Further, it is known that a high protein intake, particularly when coupled with exercise, is associated with improved bone strength [18], and effect that is likely modulated by the stimulating effects of dietary protein on the secretion of IGF-1 [15]. These findings lend to the idea that increased protein intake during calorie restriction may preserve the anabolic sensitivity of both skeletal muscle and bone.

However, only little is known about the underlying mechanisms, particularly pertaining to the effects of an increased protein during caloric restriction on circulating concentrations of anabolic hormones and the downstream effects on bone turnover. Therefore, the purpose of our study is to determine whether a strategy of increased dietary protein during energy deficiency can attenuate the suppression of RMR and reductions in hormones with anabolic and anti-catabolic effects on bone. For this purpose, we will conduct a prospective, randomized controlled study involving three experimental conditions: a) calorie restriction with normal protein intake (0.8 g/kg; CR-NP); b) calorie restriction with high protein intake (1.7 g/kg; CR-HP); and c) a control period of balanced caloric intake and matched protein intake (1.7 g/kg; CON).

Aim 1: To determine whether increased protein intake can preserve metabolic function and maintain anabolic sensitivity during calorie restriction

Hypothesis 1A: Weight loss will be similar following CR-HP and CR-LP, but the loss of lean mass and the suppression of resting metabolic rate will be reduced in CR-HP when compared to CR-NP.

Hypothesis 1B: The reduction in circulating concentrations of the anabolic hormones IGF-1, insulin, and testosterone will be attenuated in CR-HP when compared to CR-NP.

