Prior to study start, body composition will be assessed with a bioimpedance analyser (Bodystat Quadscan 4000). Peak oxygen uptake (VO₂peak) will be assessed using an incremental exercise test on a bicycle ergometer (Monark LC6).

4. Randomization

Each participant will be randomly assigned to one of the six possible permutations of the order of the study conditions (CON/CR-LP/CR-HP). Randomization of study condition order will occur in blocks of 6.

5. Nutritional intervention:

After randomization of study condition order, participants will proceed through each of the following conditions. Each condition will last 5 days with a post-test on day 6:

CR-LP: Participants will consume 30 kcal/kg FFM/day and 0.8 g protein/kg BW/day.

CR-HP: Participants will consume 30 kcal/kg FFM/day and 1.7 g protein/kg BW/day.

CON: Participants will consume 55 kcal/kg FFM/day and 1.7 g protein/kg BW/day.

Dietary energy intake prescriptions will be controlled individually utilizing a combination of two clinical products (Ensure Original and Ensure High Protein, both Therapeutic Nutrition, Abbot) and maltodextrin (Tate & Lyle) such that the target energy intake of 30 kcal/kg FFM/day (CR-LP and CR-HP) or 55 kcal/kg FFM/day (CON) is reached. Participants will be provided clear plastic bottles each day with the prescribed amount of the clinical products and will be asked to consume all of it during the day.

6. Prescribed Exercise

During each conditions, participants will conduct daily supervised exercise on a bicycle ergometer (Monark LC6) at an exercise intensity of 60% VO₂peak. Exercise duration will be adjusted individually such that exercise energy expenditure will amount to 15 kcal/kg FFM/day. Exercise will take approximately 60-90 minutes. Additional exercise and intense physical activity will be prohibited. Compliance will be monitored using an activity monitor (Actigraph). Activity monitors will be returned at the end of each study period.

7. Washout

Once a participant completes a study condition, they will be allowed a washout period before beginning the next study condition. Washout periods between conditions will be 14 days to allow protein balance to return to baseline (Hoffer & Forse, 1990). During this time, participants will resume their regular diet and physical activity. Calcium and vitamin D supplementation will continue to maintain their intake at levels required for optimal bone health.

8. Assessments

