All assessments will be identical during each study condition, which lasts for 5 days and includes post testing on day 6. On day 1 and 6, participants will arrive at the lab in the morning following an overnight fast and undergo the following assessments:

- o Bioimpedance: Body composition is assessed with a bioimpedance analyser (Bodystat Quadscale 4000). While lying in the supine position (with no parts of the body touching one another), four electrodes are attached to the wrist, hand, ankle and foot on the right side of the body. The cables from the bioimpedance analyzer are then attached to the electrodes and the device is turned on, running an electrical current through the body to estimate body composition.
- o Resting Metabolic Rate: Resting Metabolic Rate (RMR) will be measured following an overnight fast (no food or drink, except water, 12 hours before the scheduled test) between 6-10:00 a.m. and before exercise. Participants will be asked to lie supine at rest for 30 minutes in order to achieve a steady state prior to measurement. Oxygen consumption and carbon dioxide production will then be measured with a ventilated hood system (COSMED Quark CPET Metabolic Testing System) for 30-45 minutes. For the determination of RMR, only data during steady state will be used, which is defined as variations in oxygen uptake, carbon dioxide production of less than 10%, and in respiratory quotient by less than 5% for at least 10 minutes. RMR will be calculated from oxygen uptake and carbon dioxide production using the Weir equation (Weir, 1949).
- o Fasting Blood Collection: A fasting blood sample will be collected from a forearm vein by trained personnel.
- o VO₂peak: Participants will be asked to complete a graded cycle ergometer test to determine aerobic fitness (VO₂ peak). Participants will begin cycling on the bicycle ergometer at 60 W for 3 minutes. The work rate will be increased by 35 W every 3 minutes until exhaustion (Achten & Jeukendrup, 2003). Exhaustion is operationally defined when at least two of the following are met: 1) 90% age predicted heart rate max [220-age], 2) respiratory exchange ratio 1.1, 3) a rate of perceived exertion 19, 4) a plateau in VO₂ despite an increase in workload, 5) and/or unable to maintain a pedal rate of 60 rpm. During the test, expired gases will be measured through indirect calorimetry (COSMED Quark CPET Metabolic Testing System), and heart rate will be monitored through telemetry (Garmin).

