- o Questionnaires: The Three-Factor Eating Questionnaire, a questionnaire that measures three dimensions of human eating behavior (cognitive dietary restraint, disinhibition, hunger) (Stunkard & Messick, 1985), The Profile of Mood States (POMS), a questionnaire used to assess overall mood. This

profile describes six sub-components of the overall mood construct: anger, confusion, depression, fatigue, tension and vigor (McNair et al., 1971); an abbreviated version of the Eating Disorder Inventory, a self-report questionnaire used to assess the presence of eating disorders (D. M. Garner & Olmstead, 1991; David M. Garner, Olmstead, & Polivy, 1983); Satiety/Hunger Questionnaire: Participants will complete a visual analog scale (VAS) which quantifies 1) appetite, 2) fullness, 3) perception of quantity of food which can be eaten, 4) nausea, 5) thirst, and 6) stress

3. Describe how long, in terms of time, the procedures will take the participant to complete. The description should include the duration of a session, the number of sessions, over what period of time and the total time required to complete the procedures.

Following screening, the study will take at least 9 weeks to complete:

- 2 week pre-study period for preliminary testing and calcium/vitamin D equilibration
- 6 days per study condition (3x)
- Minimum 2 weeks between study conditions (2x)

4. Statistical Analysis Plan

Paired one-sided t tests will be used to assess whether changes from baseline are significantly different from 0. Where significant differences from 0 exist and differences between groups would be expected, additional t tests will be used to compare change scores between CR-LP and CR-HP or CR-HP and CON. Differences between CR-LP and CON will not be evaluated due to the existence of two manipulated variables (protein and kcal) causing the difference in those groups. If exploratory analyses are conducted, multiple comparisons will be corrected for using Holm's sequential version of the Bonferroni correction (Holm S 1979).

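### The condition contrasts use raw change scores; adjusting for each period's day-1 value is an optional, low-cost gain in precision when the within-participant day-1/day-6 correlation is low or moderate

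*Combined protocol and SAP*

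**What the plan says.** The design is a three-period crossover. Under section 2, item 4 (Randomization), "Each participant will be randomly assigned to one of the six possible permutations of the order of the study conditions". Under section 2, item 8 (Assessments), the same measurements are made at the start and end of each condition: "On day 1 and 6, participants will arrive at the lab in the morning following an overnight fast". Each outcome assessed there therefore has a day-1 and a day-6 value in each of the three periods.

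Section 4 (Statistical Analysis Plan) first tests each condition's change against zero: "Paired one-sided t tests will be used to assess whether changes from baseline are significantly different from 0". It then states that "additional t tests will be used to compare change scores between CR-LP and CR-HP or CR-HP and CON". It names no covariate and no regression or mixed model. Pairing is stated only for the tests against zero; for the contrasts it is assumed here. The documents give no total sample size, SD, alpha, power or correlation.

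**The concern.** Subtracting the day-1 value gives it a weight of exactly 1. When day-1 and day-6 variances are equal, the most precise weight is r, the correlation between day 1 and day 6 around the participant's own stable level. If r is well below 1, subtraction carries day-1 noise into the contrast. Below r = 0.5, the change score is less precise than the day-6 value alone.

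At stake is the power for CR-HP against CR-LP (called CR-NP in the hypotheses) and for CR-HP against CON, which could be lower than the collected data allow. Validity is not at stake.

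**Working it through.** **Inputs.** From the documents: three conditions per participant, all six orders, day-1 and day-6 values in each period, t tests on change scores. Assumed, because the documents give no values: n = 6 or 12 complete participants; r = 0.2, 0.5, 0.8; within-participant single-day SD of 1; a true contrast of 0.8 SD; one-sided 5%; paired contrasts; errors independent across periods. The plan states no figure to reproduce.

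**Variance per participant of a two-condition contrast.** The stable participant level cancels. With equal variances:
- change score: 2 + 2 − 4r = 4(1 − r)
- day-6 difference adjusted for day-1 difference: 2(1 − r²)
- day 6 alone: 2

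The ratio of adjusted to change score is (1 + r)/2: 0.60, 0.75 and 0.90. The ratio of change score to day 6 alone is 2(1 − r): 1.6, 1.0 and 0.4.

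**Cost of estimating the slope.** Regressing one pair's day-6 difference on its day-1 difference multiplies the ratio by (n − 2)/(n − 3). At n = 12 this is 10/9; at n = 6 it is 4/3. Setting the product to 1 gives break-even r = (n − 4)/(n − 2): 2/4 = 0.50 at n = 6 and 8/10 = 0.80 at n = 12.

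**Power.** For the paired change-score test at n = 12, the noncentrality is 0.8√12/√(4(1 − r)) = 1.55, 1.96 and 3.10 on 11 df. The adjusted analyses were simulated with 20,000 trials per setting.

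| r | Variance ratio, n = 6 | Variance ratio, n = 12 | Power, change score (n = 12) | Power, day-1 adjusted, pair by pair | Power, pooled model |
|---|---|---|---|---|---|
| 0.2 | 0.80 | 0.67 | 42% | 56% | 59% |
| 0.5 | 1.00 | 0.83 | 58% | 64% | 68% |
| 0.8 | 1.20 | 1.00 | 90% | 89% | 92% |

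The variance ratios are for the pair-by-pair regression. The pooled model has fixed participant, condition, period and day-1 value, with 2n − 5 = 19 residual df at n = 12. Its extra power comes from pooling error over three conditions, not from the covariate. With equal variances, all three methods held one-sided type I error near 5%.

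**If day-6 variance doubles in both restriction conditions** (r is the correlation before the increase). For CR-HP against CR-LP, pair by pair at n = 12:
- Extra variance unrelated to day 1: [2(1 − r²) + 2]/[4(1 − r) + 2] × 10/9 = 0.84, 0.97, 1.08.
- Day-6 deviations scaled up by √2: 4(1 − r²)/[6 − 4√2 r] × 10/9 = 0.88, 1.05, 1.09.

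The gain survives at r = 0.2, is nearly gone at 0.5 and is negative at 0.8. The pooled model's one-sided type I error for this contrast rises to about 6–7%; the paired t test and the pair-by-pair regression stay near 5%.

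**Which correlation counts.** If stable levels have k times the single-day SD, the raw correlation across people is (k² + r)/(k² + 1). At k = 3 and r = 0.5 that is 9.5/10 = 0.95. A high raw correlation, as is plausible for body mass or resting metabolic rate, does not show that r is high.

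**The case against.** The strongest reply is that nothing is broken. The hypotheses concern losses, reductions and increases; Hypothesis 1A, for example, expects that "the loss of lean mass and the suppression of resting metabolic rate will be reduced in CR-HP when compared to CR-NP". A change score estimates exactly that, and order is randomised over all six permutations. This stands, and it makes the point optional. It does not rule out adjustment: using the change as the response in the same day-1-adjusted model gives identical contrasts and standard errors.

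Second, the benefit depends on r, n and the variance pattern, none of which the documents supply. This also stands. With about 6 participants, high r or more variable responses under restriction, there may be no gain or a small loss.

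Third, a residual effect of the previous condition that shifts day 1 and day 6 equally is removed fully by the change score but only in part by an adjusted analysis, whose slope is near r. With a residual c after either restriction condition, CON follows restriction in 4 of 6 orders and CR-HP in 2 of 6. The adjusted CR-HP against CON contrast then shifts by about (1 − r)c/3. If the residual has gone by day 6, the change score shifts by c/3 and the adjusted contrast by only about rc/3. The documents do not show which case applies.

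Three stronger readings are tempting. A reader might infer that the planned contrasts are biased or inflate type I error; if they are paired, they do not. A reader might infer that they will be unpaired, because section 4 calls the conditions groups; the text leaves this open and does not say so. A reader might credit the whole rise from 58% to 68% at r = 0.5 to baseline adjustment; only the step to 64% comes from the covariate. The significance gate, sidedness and adequacy of washout are separate issues and form no part of this claim.

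**Conclusion.** The point holds as an optional improvement, not as an error. The planned contrast, if paired, is valid and answers the stated hypotheses. Adjustment for the period's day-1 value would probably sharpen it for outcomes with low or moderate r, given about 12 or more participants and roughly equal day-1 and day-6 variance. Under those assumptions at n = 12, the variance falls by about a third at r = 0.2 and a sixth at r = 0.5, worth about 14 and 6 points of one-sided power for a 0.8 SD contrast. At r = 0.8 nothing is gained. Confidence in the mechanism is high; confidence that this trial would benefit is moderate, because its n, r and variances are not in the documents.

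**What to change.** In section 4, without sight of the outcome data, prespecify that the two planned contrasts (CR-LP against CR-HP, CR-HP against CON) are within-participant and adjusted for the period's day-1 value. Either of two forms will do:
- For each pair, regress the day-6 difference on the day-1 difference; the intercept is the contrast. This form does not rely on equal variance across conditions.
- If variances are similar across conditions, fit one linear model of the day-6 value with fixed participant, condition, period and day-1 value. Fixed participant effects keep the slope within-participant.

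Keep the paired change-score test as a sensitivity analysis; it also protects against a residual effect that persists from day 1 to day 6.

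The cost is SAP wording and degrees of freedom: one in the pair-by-pair form (10 rather than 11 at n = 12), and a covariate and two period terms in the model. No new data are needed. The downside is little gain or a small loss at high r or with about 6 participants, and only partial removal of a persisting residual effect.

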Informed Consent: The researcher (or designee) obtaining informed consent will thoroughly review the consent form with each participant and confirm that the participant understands all study procedures and potential risks and benefits of study participation.

Initial Anthropometric Measurements: After obtaining informed consent, participants will be weighed to the nearest 0.1 kg on a digital scale in the laboratory with a standard outfit of t-shirt and gym shorts. Participants also will have their body fat percentage determined using caliperometry. A skinfold caliper will be used to take measurements of skinfold thickness at 7 sites (abdomen, triceps, chest, midaxillary, subscapular, suprailliac, and thigh). The skinfold measurements will be used to calculate body density and body fat percentage (ACSM's Guidelines for Exercise Testing and Prescription, Ninth Edition).

Questionnaires: Participant will then fill out the following questionnaires:

- o The Eating Disorder Inventory a self-report questionnaire used to assess the presence of eating disorders (D. M. Garner & Olmstead, 1991; David M. Garner, Olmstead, & Polivy, 1983).
- o The Health Exercise and Nutrition Questionnaire, which includes questions regarding demographics, medical history, current and past exercise, bone health, stress fracture history, current medication and supplement use, and dietary habits.
- o The Brief Calcium Assessment Tool, a brief questionnaire used to assess habitual dietary calcium intake (Yang, Martin, & Boushey, 2010).
- o The Bone-Specific Physical Activity Questionnaire, a questionnaire used to predict. The BPAQ predicted indices of bone strength at clinically relevant sites in both men and women (Weeks & Beck, 2008)
- o Absolute and Relative Contraindications to Exercise Testing, a questionnaire pertaining to absolute and relative contraindications to exercise testing to determine if the participant is able to exercise adequately (ACSM's Guidelines for Exercise Testing and Prescription, Ninth Edition).

After admittance into the study, participants will be provided with an over-the-counter calcium and vitamin D supplement. Supplementation of calcium and vitamin D will be initiated at least 2 weeks prior to the start of the first intervention to maintain the participants intake at levels required for optimal bone health.

3. Preliminary testing

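### Condition order is randomised over six sequences, but the condition contrasts are t tests on change scores with no period term, so a period effect on the five-day response would cost power and could shift the estimate if completers are unbalanced

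*Combined protocol and SAP*

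**What the plan says.** **Design.** Section 2, item 4 (Randomization) assigns each participant to one of the six orders of CON, CR-LP and CR-HP, and adds that "Randomization of study condition order will occur in blocks of 6". Section 2, item 8 (Assessments) gives every condition its own pre and post measurement: "On day 1 and 6, participants will arrive at the lab in the morning following an overnight fast and undergo the following assessments".

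**Analysis.** Section 4 first tests changes within each condition: "Paired one-sided t tests will be used to assess whether changes from baseline are significantly different from 0". It then states that "additional t tests will be used to compare change scores between CR-LP and CR-HP or CR-HP and CON". For this second step it does not say whether the tests are paired or whether they are one-sided. Nothing in the section mentions period or sequence, and there is no rule for participants who miss a condition. The word baseline is not defined. Day 1 of each condition is the natural reading, but preliminary testing also measures body composition and VO₂peak.

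**Timing.** Item 2 (Informed Consent and Screening Visit): "Supplementation of calcium and vitamin D will be initiated at least 2 weeks prior to the start of the first intervention". Item 7 (Washout): "Washout periods between conditions will be 14 days to allow protein balance to return to baseline". Section 3: "Following screening, the study will take at least 9 weeks to complete".

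**The concern.** Randomising order over all six sequences makes condition and period separable, but the analysis does not separate them. Each participant's difference between two conditions also contains the difference between the two periods in which they fell. With balanced sequences these period differences average out of the estimate but stay in its error variance. With unequal numbers of completers per sequence they do not fully average out, and part of a period effect is read as a protein or calorie effect.

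A period effect on the five-day response is plausible, though the documents do not show one. Every condition repeats five days of supervised cycling of roughly 60 to 90 minutes, and a VO₂peak test to exhaustion is listed among the day 1 and day 6 assessments. A third exposure to the same load may therefore produce a different response from the first. A level that is still settling along a curve in period 1 would have a similar effect.

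Both planned contrasts, and so both aims, are affected.

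**Working it through.** **Inputs from the documents.** Three periods and six orders; blocks of 6; days 1 and 6 measured in every condition; a 14-day washout twice; a 2-week pre-study period.

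**Inputs assumed.** The documents give no sample size, SD, alpha, effect size or dropout rate, so there is no power figure to reproduce. I take 12 participants (some results for 24), two-sided alpha 0.05, and a period effect on the change score that is linear at d SDd per period. SDd is the SD of the paired difference without a period effect.

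**Duration check.** 14 + 3×6 + 2×14 = 60 days = 8.6 weeks, which agrees with the stated minimum of 9 weeks after rounding up. The three periods themselves span 18 + 28 = 46 days, or 6.6 weeks.

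**1. Period gap by sequence** (period of CR-HP minus period of CR-LP)

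| Order | Gap | Gap² |
|---|---|---|
| CON, CR-LP, CR-HP | +1 | 1 |
| CON, CR-HP, CR-LP | −1 | 1 |
| CR-LP, CON, CR-HP | +2 | 4 |
| CR-LP, CR-HP, CON | +1 | 1 |
| CR-HP, CON, CR-LP | −2 | 4 |
| CR-HP, CR-LP, CON | −1 | 1 |

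The gaps sum to 0, so balanced sequences give no bias. The mean squared gap is 12/6 = 2, so the variance is SDd²(1 + 2d²). CR-HP against CON has the same set of gaps.

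**2. Balanced sequences**

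- Variance factor: 1.02, 1.125, 1.5 and 3.0 at d = 0.1, 0.25, 0.5 and 1.
- Participants for 80% power at a difference of 0.8 SDd, normal approximation: (1.96 + 0.84)²/0.8² = 12.25, so 13. Multiplied by 1.125, 1.5 and 3 this becomes 14, 19 and 37.
- Simulated power of the paired t test, 12 participants, true difference 1 SDd: 0.88, 0.86, 0.76 and 0.58 at d = 0, 0.25, 0.5 and 0.75.
- Simulated type I error, 12 participants: 0.048, 0.037, 0.017 and 0.001 at d = 0, 0.25, 0.5 and 1. The test becomes conservative.

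**3. Unbalanced completers**

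- Worst case for 2 lost of 12: both had the order CR-LP, CON, CR-HP. The remaining gaps sum to −4 over 10 people, so the shift is −0.4d, or −0.20 SDd at d = 0.5. Losing both with the mirror order gives +0.4d.
- Other worst cases: 2/11 = 0.18d for 1 lost of 12; 5/9 = 0.56d for 3 of 12; 4/22 = 0.18d for 2 of 24.
- Random loss of 2 of 12, over all 66 pairs: mean shift 0, SD 0.19d. At d = 0.5 that is about 0.10 SDd, against a standard error near 1/√10 = 0.32 SDd.

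**4. Drift in level rather than in response**

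- Linear drift adds the same increment to each day 1 to day 6 change, so it cancels.
- Exponential drift of total size A and time constant τ adds A(1 − e^(−5/τ)) to the period 1 change. Period 3 starts 40 days later, so the period 1 minus period 3 remainder is A(1 − e^(−5/τ))(1 − e^(−40/τ)): 0.39A, 0.19A and 0.07A for τ = 10, 20 and 40 days.

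**5. Adjusted analyses, 12 participants**

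- Paired differences regressed on period differences: residual df 12 − 3 = 9 instead of 11. Power for a difference of 1 SDd is about 0.87 at every d, and type I error stays at 0.05.
- Pooled model with participant, period and condition: 20 df and power about 0.91 if residual variances are equal. With no true effect and a CON residual SD of 0.75 or 0.5 times that of the calorie-restricted conditions, its type I error for CR-HP minus CR-LP is 0.066 or about 0.09.

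**The case against.** The strongest reply is that the documents show no period effect and that the design already limits the harm. The following parts of it stand.

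- A reader might infer that any drift over the study damages the contrasts. The documents do not support that. With each condition's own day 1 as baseline, steady drift in level cancels; only a changing five-day response or a curved drift matters. If baseline meant the preliminary test, level drift would enter in full.
- A reader might infer more false positives. With balanced sequences the opposite holds: type I error falls.
- A reader might infer a systematic bias. The 0.4d shift is a worst case, one pair of 66 in each direction. Nothing in the documents suggests that loss depends on sequence.
- The supplement run-in is a mitigation. It lasts at least 2 weeks, is described as equilibration, and supplementation continues through the washouts.
- Exercise is prescribed identically in all conditions, relative to VO₂peak and at a fixed energy cost.
- Justifying the washout by protein balance alone raises a question of carryover. A period term does not remove carryover, so this is no argument for one.
- The larger values of d are demanding. At d = 0.5 the shift from period 1 to period 3 is 1 SDd, as large as the treatment difference assumed in the power figures.
- The usual remedy, a pooled equal-variance model, has its own risk (step 5).

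What the reply does not answer is that the analysis leaves period unadjusted although the design allows adjustment at almost no cost, and leaves both pairing and baseline unstated.

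**Conclusion.** The point holds as a conditional loss of efficiency, together with a possible shift in the realised estimate. It does not show that the planned contrasts are invalid. If the five-day response changes by 0.1 to 0.25 SDd per period, the cost is slight: 2% to 12.5% more variance. At 0.5 SDd it is material: 50% more variance, and power of 0.76 instead of 0.88 with 12 participants and a true difference of 1 SDd. An added shift of up to 0.4d needs two losses of 12 concentrated in one extreme sequence, and it averages to zero under loss unrelated to sequence.

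All of this assumes that the between-condition tests are paired and that baseline is day 1 of each condition. The plan states neither. If the tests were unpaired, more would be lost: with 12 participants, no period effect, a difference of 0.8 SDd and an assumed within-person correlation of 0.5, simulated power is 0.47 against 0.71. The sample size, d and alpha are assumptions throughout. The change should be made because it is cheap, not because a period effect has been shown.

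**What to change.** Amend section 4 as follows.

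1. Define baseline as the day 1 value of the same condition.
2. State that the CR-HP against CR-LP and CR-HP against CON comparisons are within participant.
3. Adjust each comparison for period in one of two ways:
   - regress each participant's difference in change score on the period-difference indicators (for periods 2 and 3: the indicator that the first condition fell in that period, minus the same indicator for the second) and take the intercept as the contrast; or
   - fit a model with participant, period and condition that lets residual variance differ by condition.
4. Report both contrasts with confidence intervals, and the number of completers by sequence.
5. As a descriptive check on carryover, which the period term does not address, day 1 values may be tabulated by preceding condition.

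**Cost.** Wording only, with no new data. The paired regression spends two degrees of freedom; with 12 participants and no period effect, power is about 0.87 against 0.88. It protects CR-HP minus CR-LP from a different variance under CON. A pooled equal-variance model offers more degrees of freedom (20 against 11), but it should not be used unchecked, because its type I error can reach about 0.09.
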